7.1.4. Serious Adverse Events (SAEs)

Serious adverse events (SAEs) will be identified and captured as SAEs if the AEs met the definitions of SAEs that were specified in the study protocol. SAEs captured and stored in the clinical database will be reconciled with the SAE database from then Gilead Pharmacovigilance and Epidemiology (PVE) Department before data finalization.

7.1.5. Treatment-Emergent Adverse Events

7.1.5.1. Definition of Treatment-Emergent Adverse Events

AEs which meet at least one of the following criteria are defined as Treatment-Emergent Adverse Events (TEAEs):

- Any AEs with onset dates on or after the start of study treatment and up to 30 days after the permanent discontinuation of the study treatment
- Any AEs leading to permanent discontinuation of study treatment

7.1.5.2. Incomplete Dates

If the onset date of the AE is incomplete and the AE stop date is not prior to the first dosing date of study drug, then the month and year (or year alone if month is not recorded) of onset determine whether an AE is treatment emergent. The event is considered treatment emergent if both of the following 2 criteria are met:

- The AE onset is the same as or after the month and year (or year) of the first dosing date of study drug, and
- The AE onset date is the same as or before the month and year (or year) of the date corresponding to 30 days after the date of the last dose of study drug

An AE with completely missing onset and stop dates, or with the onset date missing and a stop date later than the first dosing date of study drug, will be considered to be treatment emergent. In addition, an AE with the onset date missing and incomplete stop date with the same or later month and year (or year alone if month is not recorded) as the first dosing date of study drug will be considered treatment emergent.

In case when the AE onset date is incomplete and needs to be imputed, the following algorithm will be followed:

- If day is missing but the month and year are available, then the imputed day will be the first day of the month or the first dosing date if they have the same month and year, whichever is later.
- If day and month are missing but year is available, then the imputed day and month will be 01Jan or the first dosing date if they have the same year, whichever is later.

7.1.6. Summaries of Adverse Events and Deaths

Treatment-emergent AEs will be summarized based on the Safety Analysis Set.

7.1.6.1. Summaries of AE Incidence by Severity

The number and percentage of subjects who experienced at least 1 TEAE will be provided and summarized by SOC, HLT, PT, and treatment group. For other AEs described below, summaries will be provided by SOC, PT, and maximum severity:

- TEAEs
- TEAEs of Grade 3 or higher
- Treatment-related TEAEs by study drugs (ie ENTO, VCR, dexamethasone, CNS prophylaxis)
- Treatment-related Grade 3 or higher TEAEs by study drugs

- TE SAEs
- TE treatment-related SAEs by study drugs
- TEAEs leading to treatment discontinuation by study drugs
- TEAEs leading to treatment reductions or interruptions by study drugs
- TEAEs leading to death
- TEAEs leading to study discontinuations

A brief, high-level summary of AEs described above will be provided by the number and percentage of subjects who experienced the above AEs.

Multiple events will be counted only once per subject in each summary. Adverse events will be summarized and listed first in alphabetic order of SOC, and then by PT in descending order of total frequency within each SOC. For summaries by severity, the most severe severity will be used for those AEs that occurred more than once in a given subject during the study.

In addition, data listings will be provided for the following:

- All AEs, indicating whether the event is treatment emergent
- All AEs of Grade 3 or higher
- All SAEs
- Deaths
- All AEs leading to study treatment discontinuation by study drugs

7.1.6.2. Summary of Deaths

A summary (number and percentage of subjects) of deaths will be provided by treatment group. Summary will include the following categories:

- All deaths
- Deaths within 30 days of the last dosing of study drug
- Deaths beyond 30 days of the last dosing of study drug

7.1.7. Dose Limiting Toxicity

Dose limiting toxicity (DLT) will be analyzed using DLT analysis set.

A listing of the DLT AEs will be provided by dose level, subject identification, actual dose amount prior to or on the start date of the AE, DLT terms from the investigators, CTCAE terms, and associated severity grade, if available.

7.2. Laboratory Evaluations

Laboratory data collected during the study will be analyzed and summarized using both quantitative and qualitative methods. Summaries of laboratory data will be provided for the Safety Analysis Set and will include data collected up to the last dose of study drug plus 30 days. The analysis will be based on values reported in conventional units. When values are below the LOQ, they will be listed as such, and the closest imputed value will be used for the purpose of calculating summary statistics as specified in Section 3.7. Hemolized test results will not be included in the analysis, but they will be listed in by-subject laboratory listings.

A by-subject listing for laboratory test results will be provided by subject ID number and visit in chronological order for hematology, serum chemistry, and urinalysis separately. Values falling outside of the relevant reference range and/or having a severity grade of 1 or higher on CTCAE severity grade will be flagged in the data listings, as appropriate.

No formal statistical testing is planned.

7.2.1. Graded Laboratory Values

CTCAE Version 4.03 will be used to assign toxicity grades (0 to 4) to laboratory results for analysis. Grade 0 includes all values that do not meet the criteria for an abnormality of at least Grade 1. For laboratory tests with criteria for both increased and decreased levels, analyses for each direction (ie, increased, decreased) will be presented separately. Local labs will be graded based on central lab normal ranges with in-house macro. In the event that both central and local lab results are collected in the clinical database, the worst toxicity grade will be used for the summary of lab toxicities. All central and local laboratory values will be listed.

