6.2.6. Laboratory Assessments

All samples collected in this study for laboratory assessments will be sent to the central laboratory with the exception of urine pregnancy test which will be completed at the site. Screening laboratory samples should be obtained within 7 days prior to the first dose of study drug. If the samples were obtained more than 7 days prior to first dose of study drug, only the hematology and chemistry lab samples must be repeated. Local laboratory results may be used for eligibility evaluation while pending central laboratory results.

The central laboratory will be responsible for chemistry, CBC, coagulation, urinalysis, and serum pregnancy testing per Table 6-1. Any samples collected per the Study Procedure Table (Appendix 2) may be analyzed for any tests necessary to ensure subject safety. Specific instructions for processing, labeling, and shipping samples will be provided in a central laboratory manual. The date and time of sample collection will be reported to the central laboratory.

Serum Chemistry	Hematology	Other
Sodium Potassium Chloride Lipase Amylase Bicarbonate Creatinine BUN Phosphorus LDH ^a Uric acid ^a Magnesium ^a Total bilirubin Indirect Bilirubin Direct Bilirubin ALT AST Alkaline phosphatase CPK ^b	Hemoglobin Hematocrit Red Blood Cell (RBC) count White Blood Cell (WBC) Count Neutrophils Lymphocytes Monocytes Eosinophils Basophils Platelets Urinalysis Coagulation Prothrombin Time APTT INR	 Pharmacokinetic Sampling Biomarker Sampling Syk and relevant down-stream signaling pathways mechanisms of resistance PBMC Bone Marrow Aspirate Bone Marrow Biopsy
Pregnancy Testing	Virology	
Serum Qualitative β-HCG or FSH ^a Urine pregnancy test	Hep B Hep C HIV	

Table 6-1.	Analytes
------------	----------

a Screening only

b At Screening, Day 1 of each cycle and End of Treatment

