3.8. Analysis Visit Windows

3.8.1. Definition of Study Day

Study day will be calculated from the first dosing date of study drug and derived as follows:

- For post-treatment study days: Assessment Date – First Dosing Date + 1
- For days prior to the first dose: Assessment Date – First Dosing Date

Therefore, Study Day 1 is the day of first dose of study drug administration.

Baseline is defined as the last non-missing record on or prior to the date/time of the first dose of study treatment, unless otherwise specified.

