7.2.1.1. Treatment-Emergent Laboratory Abnormalities

Treatment-emergent laboratory abnormalities are defined as values that increase at least 1 toxicity grade from baseline at any postbaseline time point, up to and including the date of last dose of study drug plus 30 days. If the relevant baseline laboratory value is missing, any abnormality of at least Grade 1 observed within the time frame specified above will be considered treatment emergent.

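### Grading local laboratory results on central normal ranges can misgrade ULN-based tests, in either direction, in the descriptive laboratory tables

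*SAP*

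**What the plan says.** SAP 7.2.1 sets the grading scale: "CTCAE Version 4.03 will be used to assign toxicity grades (0 to 4) to laboratory results for analysis". It then gives two rules for local results, neither of them qualified:

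- The range: "Local labs will be graded based on central lab normal ranges with in-house macro".
- The choice between sources: "In the event that both central and local lab results are collected in the clinical database, the worst toxicity grade will be used" in the summary of laboratory toxicities.

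The same section says that every central and local value will be listed.

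The grades feed three displays: worst postbaseline grade (SAP 7.2.1.2), shift from baseline to worst grade (SAP 7.2.2), and treatment-emergent abnormalities. SAP 7.2.1.1 defines the last as "values that increase at least 1 toxicity grade from baseline at any postbaseline time point". SAP 3.8.1 fixes the comparator: "Baseline is defined as the last non-missing record on or prior to the date/time of the first dose of study treatment". It does not say which source supplies baseline when both exist.

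Protocol 6.2.6 describes where results come from. It says "All samples collected in this study for laboratory assessments will be sent to the central laboratory", apart from the urine pregnancy test, and gives local results one stated use: "Local laboratory results may be used for eligibility evaluation while pending central laboratory results". Protocol 8.6.3 has no rule on local results.

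Elsewhere the documents do recognise the local range. Protocol Table 4-1 judges AST at screening against the institutional ULN, and the ALT row appears to share that entry.

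**The concern.** A grade defined as a multiple of the ULN is meaningful when the value and the ULN come from the same laboratory. Dividing a local value by the central ULN moves every cut-off by the ratio of the two ULNs. The plan does this for all local results, and the worst-grade rule decides which grade reaches the table.

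The two rules work together unevenly. An over-graded local value prevails over a correctly graded central result at the same time. An under-graded local value is harmless if a central result sits beside it, but it stands if there is none.

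The tests most exposed matter in this programme. Protocol 1.2.2 reports Grade 3/4 ALT/AST elevations in 14.5% of subjects in the monotherapy trial. Protocol 1.3.4 and 1.6 describe bilirubin rises attributed to UGT1A1 inhibition. With 3 to 6 subjects per dose level, one regraded subject visibly changes a column.

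**Working it through.** The plan states no figure on this point: no ULN, no number of local results and no expected rate. So there is nothing to reproduce, and the check is algebra followed by an illustration.

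**Inputs**

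- From the documents: the two rules in SAP 7.2.1, and the ALT/AST Grade 2 band of more than 3 to 5 times ULN in Protocol Appendix 3. That appendix is a dose-modification table. It is used here only because it prints a ULN-multiple band; the SAP grades on CTCAE 4.03. Its direct bilirubin row uses 1.5 and 3 times ULN, so bilirubin has the same structure with different cut-offs.
- Assumed: all ULN values, and Grade 1 starting above 1 times ULN.

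**Step 1: formula.** Let r = local ULN / central ULN. A value v equals x times the local ULN, so v = x × local ULN. The plan grades it as v / central ULN = x × r. A central cut-off of k times ULN therefore acts at k / r times the local ULN.

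**Step 2: where the 1, 3 and 5 times cut-offs act, in multiples of the local ULN**

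| r | 1/r | 3/r | 5/r |
|---|---|---|---|
| 0.8 | 1.25 | 3.75 | 6.25 |
| 0.9 | 1.11 | 3.33 | 5.56 |
| 1.0 | 1.00 | 3.00 | 5.00 |
| 1.1 | 0.91 | 2.73 | 4.55 |
| 1.25 | 0.80 | 2.40 | 4.00 |
| 1.5 | 0.67 | 2.00 | 3.33 |

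At r = 1 nothing changes. At r = 1.25 a value at 0.9 times the local ULN, which is normal, becomes Grade 1, and 4.5 times moves from Grade 2 to Grade 3. At r = 0.8 a value at 5.5 times falls from Grade 3 to Grade 2.

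**Step 3: two worked values (assumed ULNs)**

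- Over-graded: ALT 225, local ULN 50, central ULN 40. 225/50 = 4.5 (Grade 2); 225/40 = 5.63 (Grade 3). If a paired central result is Grade 2, the table still shows Grade 3.
- Under-graded: ALT 200, local ULN 35, central ULN 45. 200/35 = 5.71 (Grade 3); 200/45 = 4.44 (Grade 2). This can lower the table entry only where no central result exists.

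**Step 4: what is not touched.** Grades on absolute thresholds do not involve the ULN; an example is Grade 4 neutropenia at ANC below 500/µL (Protocol 3.5). Adverse event severity is graded by the investigator (SAP 7.1.2), and DLTs are judged and described by the investigator (Protocol 3.5, SAP 7.1.7).

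**Step 5: direction, by illustration.** A simulation with no drug effect gives the share of subjects flagged treatment-emergent on one test. Every input is assumed: median 0.6 times ULN, between-subject log SD 0.35, within-subject log SD 0.15, 10 postbaseline visits, and 5% assay error on the local result. Baseline is the central record except in the last row.

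| Setting | r = 0.8 | r = 1 | r = 1.25 |
|---|---|---|---|
| Central results only (r not used) | 13.4% | 13.4% | 13.4% |
| Local pair at 10% of postbaseline visits, worst grade | 13.4% | 13.6% | 18.4% |
| Local pair at 50% of postbaseline visits, worst grade | 13.4% | 14.4% | 29.8% |
| Local result alone at all postbaseline visits | 2.9% | 14.4% | 36.2% |
| Local pair at baseline only, worst grade | 13.4% | 12.7% | 5.4% |

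The count rises, stays level or falls, depending on r and on where local results enter. Given Protocol 6.2.6, the rows with frequent local results are stress cases and not expectations. With each result graded on its own laboratory's range, the 50% row is 14.4% whatever the ULN ratio.

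**The case against.** The strongest reply is that exposure is small and the convention is cautious. Protocol 6.2.6 sends essentially all samples to the central laboratory and mentions local results only for eligibility. Taking the worst grade is an accepted safety convention, and giving central results precedence in the main table could move a genuinely severe local value out of sight. The tables are descriptive (SAP 7.2 plans no formal testing), and all raw values are listed. This all stands. It limits the importance of the point and is why the worst-grade summary should stay. It does not repair the range rule, because a misgraded value is not made right by being the larger one, and a local value with no central partner can be under-graded.

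A second reply is that one common ULN treats equal values equally. That would hold if the laboratories measured on the same scale and their ULNs differed for other reasons. The documents do not say so, and Table 4-1 uses the institutional ULN at entry.

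A reader might infer that a local eligibility value raises the baseline grade and so hides later worsening. The documents largely answer this. Chemistry and haematology are drawn again before dosing on Lead-in Day -7 and go to the central laboratory, and baseline is the last record on or before first dose. A local screening value becomes baseline only if that draw is missing or a later local pre-dose record exists.

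**Conclusion.** The point holds as a limited defect. For ULN-based tests, the stated rule gives a wrong multiple whenever local and central ULNs differ, and possibly a wrong grade. An over-graded local value overrides a paired central result; an under-graded one matters only when it stands alone.

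The size and net direction cannot be derived. They depend on ULN ratios and on the number and timing of local results, none of which the documents give. The figures above rest on assumed ULNs and assumed variability. One regraded subject is 1/6 to 1/3 (17% to 33%) of a dose-level column, but that is true of any single event in cohorts of 3 to 6 and is not an estimate of how often this happens.

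A reader might also infer that the rule biases the primary safety result or the dose decision. The documents do not support that: DLTs and adverse event grades are the investigator's, and the 3+3 rule uses those. What can be distorted, either way, is the descriptive laboratory grade, treatment-emergent and shift tables. This is a minor point, worth correcting because the correction is cheap.

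**What to change.** In SAP 7.2.1:

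1. Grade each local result on the performing laboratory's own range where that range is available. Sites need the institutional ULN for AST/ALT eligibility, so it should exist at site level; the documents do not say whether it is in the database.
2. Where the local range is not available, keep the central range but flag the result as such in tables and listings.
3. Keep the worst-grade summary as the main display, so that a more severe local value stays visible.
4. Add a central-only sensitivity table for ULN-based tests, with baseline and postbaseline grades both taken from the central source.

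The cost is one extra table and a small programming change to the grading macro. If the SAP is already final, SAP section 1 provides for recording the change in the CSR.

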7.2.1.1. Treatment-Emergent Laboratory Abnormalities

Treatment-emergent laboratory abnormalities are defined as values that increase at least 1 toxicity grade from baseline at any postbaseline time point, up to and including the date of last dose of study drug plus 30 days. If the relevant baseline laboratory value is missing, any abnormality of at least Grade 1 observed within the time frame specified above will be considered treatment emergent.

7.2.1.2. Summaries of Laboratory Abnormalities

Summaries (number and percentage of subjects) of baseline and worst postbaseline treatment-emergent laboratory abnormalities will be provided by lab test. Subjects will be categorized according to the most severe postbaseline abnormality grade for a given lab test.

A by-subject listing will include all laboratory results with flags to indicate treatment emergent laboratory abnormalities.

7.2.2. Shift in CTCAE Grade Relative to Baseline

Shift tables will be presented by showing change in CTCAE severity grade from baseline to the worst grade postbaseline.

7.3. Body Weight and Vital Signs

A by-subject listing of body weight and vital signs will be provided by subject ID number and visit in chronological order. High or low values for vital signs will be flagged.

7.4. Prior and Concomitant Medications

Prior and concomitant medications will be coded based on World Health Organization Drug Dictionary (WHO DRUG) Version Q32017 into Anatomical-Therapeutic-Chemical classification (ATC) codes.

7.4.1. Prior Medications

Prior medications are defined as any medications taken before a subject took the first dose of study drug.

For the purposes of analysis, any medication with a start date prior to the first dosing date of study drug will be included in the prior medication summary regardless of when the stop date is. If a partial start date is entered the medication will be considered prior unless the month and year (if day is missing) or year (if day and month are missing) of the start date are after the first dosing date. Medications with a completely missing start date will be considered as prior medication, unless otherwise specified.

All prior medications will be provided in a by-subject listing sorted by subject ID number and administration date in chronological order based on FAS analysis set.

7.4.2. Concomitant Medications

Concomitant medications are defined as medications taken while a subject took study drug.

For the purposes of analysis, any medications with a start date prior to or on the first dosing date of study drug and continued to be taken after the first dosing date, or started after the first dosing date but prior to or on the last dosing date of study drug will be considered concomitant medications. Medications started and stopped on the same day as the first dosing date or the last dosing date of study drug will also be considered concomitant. Medications with a stop date prior to the date of first dosing date of study drug or a start date after the last dosing date of study drug will not be considered as concomitant. If a partial stop date is entered, any medication with the month and year (if day is missing) or year (if day and month are missing) prior to the date of first study drug administration will not be considered as concomitant medication. If a partial start date is entered, any medication with the month and year (if day is missing) or year (if day and month are missing) after the study drug stop date will not be considered as concomitant medication. Medications with completely missing start and stop dates will be considered as concomitant medication, unless otherwise specified.

The incomplete dates handling method used for AE summaries will be used for concomitant medication summaries (Section 7.1.5.2).

All concomitant medications (other than per-protocol study drugs) will be provided in a by-subject listing sorted by subject ID number and administration date in chronological order based on FAS analysis set.

7.5. Electrocardiogram Results

Electrocardiogram is not planned to be assessed for the study.

7.6. Other Safety Measures

No additional safety measures are specified in the protocol.

7.7. Changes From Protocol-Specified Safety Analyses

There are no deviations from the protocol-specified safety analyses.

8. PHARMACOKINETIC ANALYSES

Pharmacokinetic peripheral blood samples are obtained pre-dose during Lead-in on Day -7; Cycle 1 on Day 1, 8, 28 and Cycle 2 on Day 28. PK blood samples will also be collected 1.5 hours post-dose of ENTO (± 30 minutes) during Lead-in on Day -7; Cycle 1 on Days 1, 8, 28 and Cycle 2 on Day 28.

Concentrations of ENTO in plasma will be determined using a validated bioanalytical assay.

8.1. Statistical Analysis Methods

8.1.1. Plasma Concentration

The listings of ENTO PK concentrations and pharmacokinetic sampling details by subject including deviations in scheduled and actual draw time and procedures will be provided.

10. SOFTWARE

SAS[®] Software Version 9.4 or higher, SAS Institute Inc., Cary, NC, USA.

11. SAP REVISION

Revision Date (dd month, yyyy)	Section	Summary of Revision	Reason for Revision

Appendix 1 Schedule of Assessments

Study Phase	Screening (-28 days)	ENTO Lead-in*	Cycle 1					Cycle 2					Maintenance**					End of Treatment	30 Day Follow-Up
Cycle Day	Screening	-7	1	8	15	22	28	1	8	15	22	28	1	8	15	22	28		
Study Day		1	8	15	22	29	35												
Study Assessments																			
Informed Consent	X																		
General and Safety Assessments																			
Physical Exam and weight ^a	X	X	X	X	X	X	X	X	X	X	X	X	X	X	X	X	X	X	X
Vital Signs ^b	X	X	X	X	X	X	X	X	X	X	X	X	X	X	X	X	X	X	X
AE/Concomitant Meds ^c		X	X	X	X	X	X	X	X	X	X	X	X	X	X	X	X	X	X
Medical History	X																		
HBV, HCV, and HIV Virology	X																		
Smoking status	X	X	X					X					X						
Disease Assessments																			
ECOG	X	X	X					X					X					X	
Laboratory Assessments																			
Bone marrow aspirate and biopsy ^d	X			X			X					X						X	
Hematology ^e	X	X	X	X	X	X	X	X	X	X	X	X	X	X	X	X	X	X	X
Serum Chemistry & Liver Function Testing	X	X	X	X	X	X	X	X	X	X	X	X	X	X	X	X	X	X	X
Urinalysis	X		X					X					X					X	
Urine or Serum Pregnancy Test or FSH ^f	X	X	X					X					X					X	
Pharmacokinetic Sampling ^g		X	X	X			X					X							

Study Phase	Screening (-28 days)	ENTO Lead-in*	Cycle 1					Cycle 2					Maintenance**					End of Treatment	30 Day Follow-Up
Cycle Day	Screening	-7	1	8	15	22	28	1	8	15	22	28	1	8	15	22	28		
Study Day		1	8	15	22	29	35												
CSF (for PK sampling) ^h							X					X							

PPD

Imaging

CT or PET ^k (Investigator's discretion, for EMD subjects only)	X			X			X					X							
--	---	--	--	---	--	--	---	--	--	--	--	---	--	--	--	--	--	--	--

Investigational Product and Auxiliary

ENTO ^l		X	X				X	X				X	X				X		
IV Vincristine ^m			X	X	X	X		X	X	X	X		X						
Dexamethasone ⁿ				X		X		X		X			X		X				
CNS Prophylaxis per institutional standard ^o							X					X							

* For Dose Escalation only

** During Maintenance Cycle 1, all visits are required. Starting from Maintenance Cycle 2, Day 1 is required and Day 8/15/22/28 visits are per the Investigator's discretion.

- a Complete physical examination will be performed at Screening which includes height. A modified physical examination capturing changes from prior exams will be performed at other visits.
- b Vital signs (including blood pressure, respiratory rate, pulse, oxygen saturation by pulse oximetry and temperature) should be taken after the subject has been sitting for at least 5 minutes.
- c Following consent, adverse events will be assessed pre-and post-dose during each clinic visit, and 30 (±7) days following completion of the subject's last dose of study drug. Subjects should be contacted by phone (or in person, if necessary) 30 days (±7 days) after the subject's last dose of study drug to assess AEs. Subjects should be asked specifically if there are any AEs since stopping the study.
- d Bone marrow aspirate/biopsy will be taken during Screening; Cycle 1 on Day 8 and Day 28; Cycle 2 on Day 28. PPD
- e CBC with differential including PT/INR and PTT.
- f For female subjects of childbearing potential, serum testing performed at screening only. Urine pregnancy test will be performed at Lead-in on Day -7 of (escalation) or during Cycle 1 on Day 1 (expansion). Pregnancy tests will be performed on a Day 1 of each cycle thereafter.
- g Pharmacokinetic peripheral blood samples will be obtained pre-dose during Lead-in on Day -7; Cycle 1 on Day 1, 8, 28 and Cycle 2 on Day 28. PK blood samples will also be collected 1.5 hours post-dose of ENTO (±30 minutes) during Lead-in on Day -7; Cycle 1 on Days 1, 8, 28 and Cycle 2 on Day 28. CNS prophylaxis administration is independent of PK time point.

h CSF samples will be collected for pharmacokinetic analysis during Cycles 1 and Cycle 2 on Day 28 (prior to CNS prophylaxis administration).

PPD

PPD

k Subjects with EMD only, with no BM involvement will not require BM aspirate/biopsy

l Treatment with ENTO will be continuous. ENTO should be dispensed on Day 28 to include cycle break drug coverage, if necessary.

m Vincristine will be administered during Cycles 1 and Cycle 2 on Days 1, 8, 15, 22 and during Maintenance on Day 1 of each cycle.

n Dexamethasone (20 mg BID; dosed for 4 days) will be dispensed during Cycle 1 on Day 8 and Day 22 and during Cycle 2 on Day 1 and Day 15. During Maintenance, dexamethasone (20 mg QD or 10 mg BID; dosed for 4 days) will be dispensed on Day 1 and Day 15 of each cycle.

o CNS prophylaxis per institutional standard during Cycle 1 and Cycle 2 on Day 28 (± 3 days).

SAP CSR GS-US-339-1560_v1.0

ELECTRONIC SIGNATURES

Signed by	Meaning of Signature	Server Date (dd-MMM- yyyy hh:mm:ss)
PPD	Clinical Research eSigned	11-Jan-2019 00:43:50
PPD	Biostatistics eSigned	11-Jan-2019 01:19:08
